## 9 SAFETY ASSESSMENT AND REPORTING

### 9.1 Definitions

#### 9.1.1 Definition of an Adverse Event (AE)

An AE is any untoward or unfavorable medical occurrence in a human subject, including any abnormal sign (e.g., abnormal physical exam or laboratory finding), symptom, or disease temporally associated with the use of study treatment, whether or not considered related to the study treatment.

#### 9.1.2 Definition of a Serious Adverse Event (SAE)

A “Serious Adverse Event” (SAE) is defined in 21 CFR 312.32. An SAE is any adverse event that meets at least one of the following criteria

- Death;
- Life-threatening;

*Life-threatening: an adverse event is considered “life-threatening” if, in the view of either the investigator or sponsor, its occurrence places the subject at immediate risk of death. It does not include an adverse event that, had it occurred in a more severe form, might have caused death.*

- Hospitalization (initial or prolonged);
- Disability or permanent damage;
- Other important medical event.

*Important Medical Event: Events which do not fit the other outcomes, but may jeopardize the subject and may require medical or surgical intervention (treatment) to prevent one of the other outcomes. Examples include allergic bronchospasm (a serious problem with breathing) requiring treatment in an emergency room, serious blood dyscrasias (blood disorders) or seizures/convulsions that do not result in hospitalization.*

## **9.2 Methods and Timing for Assessing, Recording, and Analyzing Safety Parameters**

All safety parameters will be graded using the scales listed in the Appendices B and C.

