## 2.2 Rationale

Vaccines are typically injected using a hypodermic needle, a cost efficient, rapid and direct way for vaccine delivery. However, hypodermic needles cannot be easily used by patients themselves and patient willingness to receive vaccination is limited by pain and by needle-phobia experienced by many patients (Hamilton 1995). Spread of blood borne pathogens by needle re-use is also a major concern, especially in developing countries (Drucker 2001). Microneedles can be prepared as a low-cost patch that is simple for patients to apply for vaccine delivery targeting the many antigen-presenting cells present in the skin. A recent study at Emory University evaluated the safety, reactogenicity, acceptability, and immunogenicity of administration of influenza vaccine by microneedle patch in comparison to hypodermic needle injection. Data from this study demonstrated an excellent profile of the microneedle patch.

Data regarding the safety, reactogenicity, tolerability, and acceptability of a microneedle patch in children are lacking. The goal of this study is to evaluate the safety, reactogenicity, and acceptability of placement of a placebo microneedle patch to the skin of children. Twenty-five to 50 healthy children between the ages of 6 weeks and 24 months will be enrolled in the study. Subjects will be recruited from the general population of metro Atlanta, GA and enrolled at the Emory Children's Center, located on Emory University campus in Atlanta, GA.

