### *Placebo Microneedle Patch and Excipients*

Excipients (inactive ingredients) used to make the microneedles will be USP-grade and listed on FDA's database of Inactive Ingredients for Approved Drug Products. The final composition of the patch for Cohort 1 and Cohort 2 has not been finalized but all excipients are already in use in FDA-approved drug products (and usually at a much higher dose than will be used in the microneedle patch). Excipients are expected to include trehalose, sorbitol, histidine, maltodextrin, sodium carboxymethylcellulose, polysorbate, xylitol, polyvinyl alcohol, and/or glycerol. The total mass of excipients delivered by placebo microneedle patch will be <1.5 mg.

The microneedle patches used in the placebo study will be manufactured under low bioburden conditions and in compliance with cGMP requirements for Phase 1 clinical trials according to the *FDA's Guidance for Industry 2008: CGMP for Phase 1 Investigational Drugs*. This will be the same process and same controls as those used in the manufacture of microneedle patches investigated in the Phase 1 clinical trial of the microneedle patch for influenza vaccination carried out by Georgia Tech and the Hope Clinic.

The microneedle patch has a history of safe use in human subjects. It has been used in several IRB-approved studies at Georgia Tech in adults and has always exhibited a safe profile that typically consists of itching and/or mild erythema that subsides after a few days. Similarly, the Phase 1 trial of the microneedle patch for influenza vaccination showed that the microneedle patch was safe with no serious adverse events (SAEs) reported. No new chronic medical illnesses or influenza-like illnesses were reported with the patch.

Although the composition of the microneedle patches used in these studies was different from that of the patches for the proposed placebo study in infants and young children, the microneedle patches were made of excipients that had the same safety profile as those that will be used in this placebo study. The controls that will be used to make the infant and young children placebo patches will be at least as strict as those that were used to make the patches used in the Georgia Tech IRB studies and the initial Phase 1 clinical trial of influenza vaccine administration by microneedle patch.

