Infants and children will be enrolled by sequential age groups using an age de-escalation approach (Table 1). At least 4 infants or children from each Group must complete Day 8 without halting criteria having been met (as detailed in Section 9.5) before subjects will be enrolled into the next younger age group within a Cohort. For Cohort 1, at least the first 2 children in each Group will have the microneedle patch applied to the skin overlying the shoulder blade. If this site is well tolerated without halting criteria having been met (as detailed in Section 9.5), additional microneedle patches may be applied at a different location on the same participant and in subsequent participants to the upper arm, forearm, wrist, thigh, shin, and/or foot. For Cohort 2, microneedle patches may be applied to the

shoulder blade, upper arm, forearm, wrist, thigh, shin, and/or foot. If the first site is well tolerated in the first two children without halting criteria having been met (as detailed in Section 9.5), additional microneedle patches may be applied to the same participants and in subsequent participants.

Table 1: Cohorts and Groups of Enrolled Infants and Young Children			
Cohort	Group Age Range*	Number **	Study Product (administered Day 1 and possibly Day 8)
1	12 – 24 months	Up to 7	Microneedle formulation 1
1	5 – 11 months	Up to 6	Microneedle formulation 1
1	6 weeks – 4 months	Up to 12	Microneedle formulation 1
2	12 – 24 months	Up to 12	Microneedle formulation 2
2	5 – 11 months	Up to 12	Microneedle formulation 2
2	6 weeks – 4 months	Up to 12	Microneedle formulation 2

*\*All age ranges are inclusive. 4 children from each age group must complete Day 8 without halting criteria having been met (as detailed in Section 9.5) before subjects will be enrolled into the next younger age group.*

*\*\* Total number enrolled into each Cohort will be ≤25.*

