### 7.2 Visit 2: Day 2 (+1) Clinic Visit

The following assessments will be performed.

- Obtain interim medical history and note any changes since the last visit.
- Record concomitant medications.
- Symptom-directed physical examination, if needed.
- Vital signs: temperature and pulse.
- Examine placebo microneedle patch application site. Subjects with localized rash, scarring or evidence of infection at placebo microneedle patch application site are to be evaluated by a study investigator. Per investigator discretion, photographic documentation (refer to MOP) and dermatologic referrals may be obtained.
- Study personnel will review the memory aid information with the LAR and record all AE/SAEs.
- The follow-up acceptability questionnaire will be completed by the LAR.

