### **9.2.1 Adverse Events**

All AEs occurring while on study during the AE reporting period must be documented appropriately regardless of seriousness, severity, or causal relationship to study product administration. AEs will be recorded on the AE page of the CRF.

Solicited AEs will be collected from Day 1 (after placebo microneedle placement) through Day 8 following placebo microneedle administration (Day 15 in those receiving placebo microneedle patches 2/3). Unsolicited AEs and SAEs will be collected from Day 1 (after placebo microneedle placement) through the Day 27 – 38 end of study visit. AE details will be collected via interview with the subject LAR. Information to be collected includes event description, date of onset, severity and date of resolution/stabilization of the event. Severity and relationship to study product (either “related” or “unrelated”) must be assessed by the Investigator or sub-investigator. Signs and symptoms due to a single diagnosis will be reported as the diagnosis. For example, cough, pharyngitis, rhinitis would be reported as “upper respiratory infection”. If multiple signs/symptoms presenting simultaneously cannot be attributed to the same etiology, then each symptom should be reported separately.

Any medical condition present at the time the subject is screened, or occurring prior to placebo microneedle placement will not be considered an AE, but will be captured in the medical history form. If a preexisting condition worsens (changes in severity or quality, not consistent with the subject’s reported past history of the condition) at any time during the study, this change should be captured as an AE.

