## 9.5 Study Halting Rules

Further enrollment and placebo microneedle patch application (e.g., placebo microneedle patch 2/3 placement) to subjects will be halted if any of the following occur:

- Any death following placebo microneedle patch application.
- Any subject develops erosion, ulceration, or abscess at the administration site related to study product administration.
- Any subject develops laryngospasm, bronchospasm or anaphylaxis within 24 hours of placebo microneedle patch administration.
- Any subject experiences a placebo microneedle patch-related SAE.
- Any Grade 3 AEs or an SAE that cannot be clearly attributed to another cause.

If the study is halted, the site will immediately notify the Sponsor and the Emory IRB. Prior to recommencing enrollment, all available safety data will be reviewed by the site Investigator and the Sponsor.

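### A patch-related site infection without abscess can be graded below 3, and then neither halts the study nor bars the next younger age group

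*Combined protocol and SAP*

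**What the plan says.** **Grading.** Section 9.2: "All safety parameters will be graded using the scales listed in the Appendices B and C". Appendix B has six local rows and Appendix C five general rows. Together they are the 11 solicited symptoms of 8.1.5. Section 9.2.1 leaves severity to the Investigator or sub-investigator and adds: "Signs and symptoms due to a single diagnosis will be reported as the diagnosis". The only generic 0 to 3 scale is in 8.1.5, where it is given to the LAR for describing symptoms.

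**Halting.** Section 9.5 has five bullets. Two matter most here: "Any subject develops erosion, ulceration, or abscess at the administration site related to study product administration" and "Any Grade 3 AEs or an SAE that cannot be clearly attributed to another cause". The other three are death, airway or anaphylactic reactions within 24 hours, and a patch-related SAE. After a halt, the investigator and the sponsor must review all safety data before enrollment restarts.

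**Age gate.** Section 4: "At least 4 infants or children from each Group must complete Day 8 without halting criteria having been met", and only then may the next younger group be enrolled.

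**Infection is foreseen.** It has its own heading among the risks in 2.3.1. Section 7.2 says: "Subjects with localized rash, scarring or evidence of infection at placebo microneedle patch application site are to be evaluated by a study investigator". Sections 7.3, 7.4, 7.5, 7.7 and 7.8 carry a similar instruction, which makes six visit sections.

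**The concern.** The visit schedule looks for infection at the patch site, but the grading and halting rules do not say what follows when one is found. Under 9.2.1, cellulitis is recorded as a diagnosis, and no row in the named scales fits a diagnosis. Its grade then rests on criteria that the protocol does not give. That grade decides whether the last 9.5 bullet applies.

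The participants are healthy infants and toddlers with no direct benefit (2.3.2), and Section 2.2 says: "Data regarding the safety, reactogenicity, tolerability, and acceptability of a microneedle patch in children are lacking". De-escalation from 12–24 months down to 6 weeks–4 months depends on the 9.5 criteria. A related infection that meets none of them leaves the child among the 4 who satisfy the gate, and no joint safety review is required first. Two reporting routes also depend on the grade: the 5-business-day report to the sponsor (9.3) and the monthly cumulative AE report (10.5) cover only related AEs of Grade 3 or higher.

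**Working it through.** **1. Rows available.** Appendix B: induration/swelling, erythema, ecchymosis, tenderness, pain, pruritus (6). Appendix C: irritability, lethargy, decreased appetite, vomiting, fever (5). 6 + 5 = 11. Rows for infection: 0. Rows for unsolicited AEs in general: 0.

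**2. A test case.** A 15-month-old has a cellulitis judged related to the patch. Redness is 8 cm across. There is no erosion, ulceration or abscess, no marked discomfort at rest and no fever above 102.1 F, and swelling is not above 10 cm. The child keeps to the usual routine and takes an oral antibiotic at home.

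- Graded by its redness (Appendix B, 5.1–10 cm): Grade 2.
- Graded on the 8.1.5 scale: Grade 1 or 2, because Grade 3 requires that routine activity stops.

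**3. The test case against 9.5.**

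- Death: no.
- Related erosion, ulceration or abscess: no.
- Laryngospasm, bronchospasm or anaphylaxis: no.
- Patch-related SAE: no, unless the event is judged an important medical event under 9.1.2.
- Grade 3 AE or SAE not clearly due to another cause: no, on the same condition.

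Result: 0 of 5 bullets met. The Section 4 gate refers only to these criteria, so it is not closed. Section 9.5 has no rule that counts events below Grade 3, so several such cases would not close it either.

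**4. Where the event does appear.** Three places pick it up: the third secondary endpoint (AEs at the patch site, any grade), the 11.3 tables by severity and relationship, and 9.4, which withholds patches 2/3 while an AE of Grade 1 or more is ongoing. None of these stops de-escalation.

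**5. How often it might matter.** The protocol gives no infection rate in children, so there is no figure of its own to reproduce on this point. The event probabilities in 11.2 concern rates of 5% and 10% and are not used here. Let p be the chance that a child has a related site infection treated with a systemic antibiotic. It is assumed to be 0.5%, 1% or 2%, with children independent.

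Chance of at least one in a cohort of 25 is 1 − (1 − p)^25:

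- p = 0.5%: 1 − 0.995^25 = 11.8%
- p = 1%: 1 − 0.99^25 = 22.2%
- p = 2%: 1 − 0.98^25 = 39.7%

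Two gates per cohort, each at the minimum of 4 children, involve 2 × 4 = 8 children. Chance of at least one among them is 1 − (1 − p)^8:

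- p = 0.5%: 1 − 0.995^8 = 3.9%
- p = 1%: 1 − 0.99^8 = 7.7%
- p = 2%: 1 − 0.98^8 = 14.9%

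**The case against.** The strongest reply is that this is a threshold the sponsor was entitled to choose. The study halts on erosion, ulceration, abscess, Grade 3 or an SAE, and an outpatient infection on an oral antibiotic is milder than those. No infections are reported in the experience cited in 2.3.1. An investigator sees every suspect site, and the sponsor may terminate for safety at any time (5.4.4). The CRF or MOP, not available here, may contain a severity scale. Much of this stands, and it limits the point.

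Four stronger readings are tempting, and the documents do not support them.

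- *Every infection treated at home falls below Grade 3.* No scale uses the place of treatment. Such an infection reaches Grade 3 if redness or swelling exceeds 10 cm, fever exceeds 102.1 F, discomfort at rest is significant, or activity is prevented. A related abscess halts at any grade.
- *The gate opens automatically.* Four completers are a necessary condition. The sponsor and investigator may still decline to proceed.
- *Omission from the first secondary endpoint is an error.* That endpoint counts Grade 3 events, so an event graded 2 is correctly left out.
- *The manufacturing statement shows a defect.* Section 2.3.1 says "The microneedle patches used in the placebo study will be manufactured under low bioburden conditions" and presents this as a control.

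Discretion does not close the gap, however. Section 9.5 exists so that certain events force a review without anyone having to choose one. It already does so for a single related erosion or a single Grade 3 AE. A related infection that needs systemic treatment belongs with these, and nothing in the protocol explains why it is left out.

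**Conclusion.** The point holds in a limited form. Under 9.2 and 9.5 as written, a related site infection without erosion, ulceration or abscess can fall below Grade 3, trigger no halt or required review, and leave the next younger group open to enrollment. This assumes that the child keeps to routine activity, that no size, fever or discomfort threshold for Grade 3 is crossed, and that the event is not judged an important medical event. It also assumes that no unseen CRF or MOP rule says otherwise.

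The weight comes from the consequence in a population without prior data, not from a known frequency. The probabilities above rest entirely on assumed rates. This is a worthwhile and cheap safety change; it does not bear on the validity of the analysis or on the sample size.

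**What to change.** 1. In the second bullet of 9.5, add a fourth item after abscess: infection treated with a systemic antibiotic. Keep the existing conditions that the event is at the administration site and related to the product. The Section 4 gate follows without further edits, because it refers to 9.5.
2. In 9.2, state that AEs not listed in Appendices B and C are graded by the Investigator or sub-investigator on the generic 0 to 3 scale of 8.1.5. This step alone would not change the test case, so the first is needed as well.

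Do not instead define an antibiotic-treated infection as Grade 3. A small infection in an active child would then count as severe, and the first secondary endpoint would lose its meaning.

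The cost is two short text edits. Severity, relationship and concomitant medications are already recorded, so visits, forms and sample size stay as they are. The real downside is a possible pause after one such infection, with the 25-child probabilities shown above. At those rates they are upper limits for extra pauses, since some of these infections would already halt as abscess, Grade 3 or SAE. Section 9.5 already provides for restart after review.

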### **9.2.1 Adverse Events**

All AEs occurring while on study during the AE reporting period must be documented appropriately regardless of seriousness, severity, or causal relationship to study product administration. AEs will be recorded on the AE page of the CRF.

Solicited AEs will be collected from Day 1 (after placebo microneedle placement) through Day 8 following placebo microneedle administration (Day 15 in those receiving placebo microneedle patches 2/3). Unsolicited AEs and SAEs will be collected from Day 1 (after placebo microneedle placement) through the Day 27 – 38 end of study visit. AE details will be collected via interview with the subject LAR. Information to be collected includes event description, date of onset, severity and date of resolution/stabilization of the event. Severity and relationship to study product (either “related” or “unrelated”) must be assessed by the Investigator or sub-investigator. Signs and symptoms due to a single diagnosis will be reported as the diagnosis. For example, cough, pharyngitis, rhinitis would be reported as “upper respiratory infection”. If multiple signs/symptoms presenting simultaneously cannot be attributed to the same etiology, then each symptom should be reported separately.

Any medical condition present at the time the subject is screened, or occurring prior to placebo microneedle placement will not be considered an AE, but will be captured in the medical history form. If a preexisting condition worsens (changes in severity or quality, not consistent with the subject’s reported past history of the condition) at any time during the study, this change should be captured as an AE.

### **9.2.2 Reactogenicity**

Reactogenicity events are reactions that are common and known to or expected to occur following the administration of the study product. Subjects LAR will be provided with a memory aid, thermometer and ruler and will be instructed to record the presence of solicited symptoms and oral temperature through Day 8 after placebo microneedle

placement (Day 15 in those receiving placebo microneedle patches 2/3). If a symptom is still present at Day 8 (Day 15 in those receiving placebo microneedle patches 2/3), the subject LAR will continue to follow that symptom until two days symptom-free. Memory aids will be reviewed and collected by study staff at follow up visits. Reactogenicity event details will be collected via review of the subject's memory aid and by interview with the subject LAR. Memory aid will not be considered source. The subject memory aid will be reviewed with the subject LAR at subsequent visits. Reactogenicity will be analyzed using Appendices B + C.

### **9.2.3 Serious Adverse Events**

SAEs will be collected from Day 1 (after placebo microneedle administration) through the end of study participation. Any suspected SAE that occurs outside of the protocol-specified follow-up period and considered to be caused by the study placebo microneedle must be reported.

### **9.2.4 Procedures to be followed in the Event of Abnormal Laboratory Test Values or Abnormal Clinical Findings**

AEs/SAEs will be followed until resolved or stable even if this extends beyond the study-reporting period. Resolution of an AE/SAE is defined as the return to pretreatment status or stabilization of the condition with the expectation that it will remain chronic.

## **9.3 Reporting Procedures**

Related AE grade 3 and above will be reported to the Sponsor within 5 business days.

### **9.3.1 Serious Adverse Event Detection and Reporting**

The following procedures will apply to all events meeting the definition of SAE as described in Section 9.1.2 SAEs:

**The site Investigator must submit an initial SAE report immediately (within 24 hours of site awareness) to the Sponsor.**

- Complete an initial SAE report form, reviewed and signed by PI or physician sub-investigator
- Initial report submitted by the PI on an expedited basis to the Sponsor
- SAEs must be reviewed and followed to resolution by a study physician
- Follow up reports submitted to document additional pertinent information and resolution of the event

### **9.3.2 Reporting to IRB**

The PI is responsible for reporting AEs to the site IRB in accordance with the IRB's requirements for expedited reporting and continuing review reporting.

